11.0 Study Withdrawal/Discontinuation

Subjects will be withdrawn from the study for failure to comply with study procedures or if they request to withdraw. Criteria for withdrawal include failure to comply with the study procedures, pregnancy, initiation of medications that affect glucose metabolism (such as atypical antipsychotics or steroids), or development of a disease that affects glucose metabolism, such as a chronic disease. In these instances, referral to appropriate specialty care will be made.

12.0 Statistical Considerations

Power analysis and Estimation of Sample Size: The sample size required for the study is based on the power calculation for the primary outcomes of 2 hour glucose concentrations. Based on preliminary our data from our ongoing DIG IT Study, IU-IRB 1403986016, we show that by reducing added sugars from 9.0% to 6.6% of energy leads to a decrease in 2 hour glycemia of 143.9 ± 9.6 to 123.7 ± 22.6 mg/dL, which is statistically significant and clinically meaningful. Specifically, a sample size of 13 will enable us to detect differences in 2 hr glucose concentrations before and after the intervention, with 80% power and $\alpha = 0.05$. With an expectation of 20% drop out, we will enroll 16 participants.

We will test the data for normalcy and calculate descriptive statistics. Skewed data will be normalized or non-parametric statistics will be used. For Aim 1, changes in glycemia, peak glucose excursions and insulin sensitivity will be assessed using paired T-tests (for normally distributed data). For Aim 2, changes in intensity of sweetness and liking for sparkling water will be assessed using mixed linear models with the participant as a repeated factor. As a secondary analysis we will assess relationship between changes in perceptions of sparkling water, SSB consumption and glycemic measures.

13.0 Statistical Data Management

Primary data will be collected via paper, phone interviews, direct electronic data capture from the TADA mobile app and stored electronically in REDCap, secure IT servers within IU-Bloomington. The storage location will be backed up automatically every day. Quality assurance steps will include: 1) built in range checks; and 2) testing of database by study team prior to moving to production mode. The following quality control methods will be used: 1) single entry with random checks of accuracy]; and 2) extraction and cleaning of data that will be used for analysis every 1 year.

14.0 Privacy/Confidentiality Issues

All paper records containing identifying information will be kept in locked offices. All computer records utilized for the study will require password access. Information utilized for study data may be stored in one or more of the following: excel spreadsheets, statistical software databases, RedCap, PResNet database. Access to the study data will be restricted to study personnel.

15.0 Follow-up and Record Retention

The duration of study record retention will be at least 7 years after the study has ended, with the possibility of indefinite archiving of study records and data.

16.0 COVID-19 Contingency Plan

Given the current situation of coronavirus and social distancing recommendations, we would also like to propose the following alternative option for our research approach, utilizing remote execution of procedures that can be performed virtually.

16.1 Remote Enrollment

We will continue the original plan of recruitment, from the Youth Diabetes Prevention Clinic, the community, as well as participants that have completed the ongoing DIG IT study and who consented that we could contact them for future studies (IU – IRB Protocol #1403986016). In

addition to these methods of recruitment, we will use social media advertisements (Facebook and Instagram) and online flyers of the study as additional sources for remote recruitment.

16.2 Study Procedures

The study procedures would be conducted in three different online sessions. The purpose of the online sessions is to ensure participants and their parents/guardians have full understanding of the study and perform the tasks as instructed, minimizing any potential risks and maximizing accuracy of results. Each online session would have up to 1 hour in duration. Details for each session are noted below.

Session 1

- 1. Consent/Accent forms.** Consent/assent forms will be mailed to potential participants. During the online session, a study investigator will review with participants and their parent/guardians all the risks and benefits of participating in the study. Upon decision of participating in the study, participants older than 14 years of age will sign the consent forms, and participants younger than 14 years will have their parents/guardians sign the assent forms. If participants consent/assent, they will sign the forms, send immediate pictures of the signature pages, and then return to us physically using a provided stamped envelope for return. If a participant does not consent/assent, we will end the session.
- 2. TADA instructions.** The TADA app will be previously installed on the iPhones provided to participants. After consent/assent, participants will be instructed on how to use the app to report their consumption of flavored seltzer water and other beverages, as well as how to take pictures of their food for the 4-day food record (every 2 weeks).
- 3. Anthropometric measurements.** Participants will be asked to weigh themselves and measure their height with the help of another person. They will also be guided on how to measure their waist circumference, as previously described (38). If participants do not have a scale or measuring tape, these items will be delivered to participants' houses.
- 4. Choosing seltzer water and soda flavors for sensory tests and 12-week intervention.** Participants will be given the option of choosing flavored sparkling water. Sugar-sweetened soda of the matching flavor will be used in the sensory tests.

In the second session, participants and their parents/guardians will be instructed on how to perform the sensory tests. After instructions are provided, the participants will execute the sensory tests, while the study personnel remains online to witness the test and provide any assistance needed by participants. Session 2 is described in further details below. Session 3 will be equal to session 2 and will happen at the end of the 12-week intervention.

Session 2

[figure not shown]
Sensory testing to measure perception of sparkling beverages. Due to the current situation with the COVID-19 pandemic, we intend to execute the sensory testing remotely. An online platform, such as Zoom, Cisco Webex, Skype or other will be used to instruct the participants and a parent or guardian about how to perform the sensory tests. No video recordings or pictures will be taken of the participants. We will ask the participants to conduct the test when they are not hungry, but when they have not consumed another food or beverages (other than water) for at least 1 hour. Flavored sparkling water and sodas will be used to conduct the sensory tests. The beverages will be ordered online

from supermarkets such Walmart, Target or Payless and the participants will have the options of home delivery or store pickup. A marked cups will also be delivered so that the parents or guardians of participants can mix the correct volume of sparkling water and soda to obtain a total of 6 levels of sweetness (plain flavored sparkling water, plain soda and 4 mixtures of sparkling water and soda that vary in sweetness intensity) in the beverages. Disposable plastic cups will also be delivered to participants to test the 6 sweetness levels. We will guide the parents through the testing procedure, instructing them which sample to give when (in order to maintain randomization of sample tasting). Participants will rate the samples for their sweetness using a "just about right" visual analog scale, with anchors at: -100, "Not sweet enough"; -50, "Slightly not sweet enough"; 0, "Just about right"; +50, "Slightly too sweet"; and +100 "Too sweet." Samples will also be rated for liking using a hedonic visual analog scale, with anchors at: -100, "Worst ever"; -50, "Dislike"; 0, "Neutral"; +50, "Like"; +100, "Best ever." Before and between each sample participants will rinse with water, and a 1-minute break will be enforced between each sample. These ratings will be collected digitally using the same iphones that we will use for the TADA app.

Below is a scheme of the remote sensory test.

Session 3

Sensory testing to measure perception of sparkling beverages. Due to the current situation with the COVID-19 pandemic, we intend to execute the sensory testing remotely. An online platform, such as Zoom, Cisco Webex, Skype or other will be used to instruct the participants and a parent or guardian about how to perform the sensory tests. No video recordings or pictures will be taken of the participants. We will ask the participants to conduct the test when they are not hungry, but when they have not consumed another food or beverages (other than water) for at least 1 hour. Flavored sparkling water and sodas will be used to conduct the sensory tests. The beverages will be ordered online from supermarkets such Walmart, Target or Payless and the participants will have the options of home delivery or store pickup. A marked cups will also be delivered so that the parents or guardians of participants can mix the correct volume of sparkling water and soda to obtain a total of 6 levels of sweetness (plain flavored sparkling water, plain soda and 4 mixtures of sparkling water and soda that vary in sweetness intensity) in the beverages. Disposable plastic cups will also be delivered to participants to test the 6 sweetness levels. We will guide the parents through the testing procedure, instructing them which sample to give when (in order to maintain randomization of sample tasting). Participants will rate the samples for their sweetness using a "just about right" visual analog scale, with anchors at: -100, "Not sweet enough"; -50, "Slightly not sweet enough"; 0, "Just about right"; +50, "Slightly too sweet"; and +100 "Too sweet." Samples will also

be rated for liking using a hedonic visual analog scale, with anchors at: -100, "Worst ever"; -50, "Dislike"; 0, "Neutral"; +50, "Like"; +100, "Best ever." Before and between each sample participants will rinse with water, and a 1-minute break will be enforced between each sample. These ratings will be collected digitally using the same iphones that we will use for the TADA app.

Anthropometric measurements. Participants will be asked to weigh themselves and measure their height with the help of another person. They will also be guided on how to measure their waist circumference, as previously described (38). If participants do not have a scale or measuring tape, these items will be delivered to participants' houses.

Title: Effect of Reducing Added Sugar Intake, By Substituting Sparkling Water, on Glycemia in Adolescents at Risk for Type 2 Diabetes

NCT05966870

Version Date: 06/28/2024

Statistical Model

Linear mixed models with participants as a repeated measure were performed using SAS OnDemand (Cary, NC) in Jupyter Lab. Full code is available in Appendix A.

The model used was:

Rating = Concentration Time Concentration*Time

Where “Rating” is the JAR/liking rating. “Concentration” is 0, 1.8, 2.8, 4.4 6.9, 10.7% w/v. “Time” is before (“Pre”) or after (“Post”) the 12-week intervention. The Kenward Rogers approximation was used for degrees of freedom and participants were incorporated as a repeated measure. Distribution of residuals was checked and met model assumptions for independence and normality. For JAR ratings, covariance structure was set to compound symmetry; for disliking/liking ratings, a variance components structure had to be used as compound symmetry failed the null model test (indicating the compound symmetry was not a better model than variance components, which is the default).

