3.2 Secondary Outcome Measures

3.2.a. Flavor Perception of Sparkling Water. We will use sensory testing to measure perception of sparkling beverages at the baseline and at the end of the study [30]. We will test a total of 6 levels of sweetness in the beverages so that we can observe if a shift in ideal level of sweetness occurs after consuming the unsweetened waters. The sparkling beverages will be labeled with randomized 3-digit codes. The participants will first taste an unsweetened and fully sweetened beverages (to control for order and desensitization effects) and then all samples (including replicates of the unsweetened and fully sweetened beverages) will be presented to participants in counterbalanced order. Participants will rate the samples for their sweetness using a "just about right" visual analog scale, with anchors at: -100, "Not sweet enough"; -50, "Slightly not sweet enough"; 0, "Just about right"; +50, "Slightly too sweet"; and +100 "Too sweet." Samples will also be rated for liking using a hedonic visual analog scale, with anchors at: -100, "Worst ever"; -50, "Dislike"; 0, "Neutral"; +50, "Like"; +100, "Best ever." Before and between each sample participants will rinse with water, and a 1 minute break will be enforced between each sample.

3.2.b. CVD Outcomes, Blood Triglycerides, Blood Pressure and Waist Circumference. We will assess these measures during study visits at the clinical centers at the same time and under fasting conditions as for the oral glucose tolerance testing. We will measure blood pressure after 5 minutes of rest, on the right arm in the supine position, using a sphygmomanometer with an appropriate sized cuff [31]. Plasma triglyceride concentrations (along with total, and low and high-density cholesterol) will be measured by the Indiana University School of Medicine Diabetes Center Translation Core laboratory (Indianapolis, IN), using established enzymatic colorimetric methods. Anthropometric measurements will include height, weight, body mass index, waist circumference, and sagittal abdominal diameter [32]. We will calculate BMI percentiles and Z-scores from age- and sex-specific reference values as defined by the Centers for Disease Control and Prevention (CDC) growth charts [33]..

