5.0 Study Design

The study design is a prospective observational study in adolescents who are at risk for developing T2D, to evaluate the effectiveness of sparkling water to reduce dietary intake of added sugars and thereby improve glycemia. Study data on consumption and the flavor profile of sparkling water will serve as a measure of acceptability. The study intervention will be to provide carbonated flavored sparkling water for 12 weeks to adolescents who have a usual intake of 2 or more servings of SSB per day and are at a high risk for developing type 2 diabetes. Study measures will be obtained before and after the exposure to carbonated flavored sparkling water and each participant will serve as his/her own control. To encourage the participants to substitute the carbonated flavored sparkling water, study personnel will send them weekly iMessages through the TADA app. In addition, we will monitor the participants' diet, using the TADA app, every two weeks, for 4 days. Study measurements will be obtained at baseline, before the intervention, during and at the end of the 12-week intervention.

Flow diagram for randomized, controlled trial

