7.0 Study Procedures

1. **Description of Intervention - Exposure to Sparkling Water:** During baseline study visit 1, participants will be provided with 4 flavors of sparkling water (1 of each flavor) to sample in the 6 days prior to the beginning of the study. Each participant will be asked to choose the his/her most preferred flavor, which will be used during the 12-week intervention. The intervention will be to provide sparkling water to all participants and ask them to substitute the water in place of sugar sweetened beverages for 12 weeks. We will work with the parents/guardians to determine whether delivery or pickup of the beverages from a store is most feasible. To encourage and remind the participants to drink the sparkling water, study personnel will send iMessages through the TADA app, once a week. To assess the consumption of the sparkling drinks, as well as total dietary intake, the participants will create food records, using the TADA app, at baseline, every two weeks and at the end of the study.
2. **Baseline. Initial Visit One - Obtaining Consent and Glycemia and Dietary Measurements:** This meeting will occur at the Clinical Research Center at Indiana University-Purdue University Indianapolis (CRC IUPUI) . The research team will meet with potential subjects to explain the study and to consent/assent the subject. If consent/assent is obtained, the study physician or study nurse will place the continuing glucose monitor. The researcher will give instruction on tracking dietary intake, using the TADA tool. The consent documents may be mailed to the potential participant prior to the training meeting in order to have time to review them. The visit will take one hour of time. During this visit, participants will also be asked about any food allergies and dietary restrictions. This information will be used to select a snack (granola or breakfast bar type item) for participants to consume before the sensory test during baseline visit two and at the final study visit two. Consumption of the snack ensure the participant is not excessively hungry

before making the sensory ratings (hunger makes energy containing foods more palatable, skewing sensory ratings).

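### The rating models described in the SAP leave out participant-specific responses, and a non-significant null-model test does not show that liking ratings are independent

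*SAP*

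**What the plan says.** The SAP (Statistical Model) gives the model for both JAR and liking ratings as "Rating = Concentration Time Concentration*Time", over six concentrations and two times, with Kenward-Roger degrees of freedom. Participants enter as a repeated measure, and no participant-by-Concentration or participant-by-Time term is described.

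The two outcomes differ in covariance structure:

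- JAR: "For JAR ratings, covariance structure was set to compound symmetry".
- Liking: "for disliking/liking ratings, a variance components structure had to be used as compound symmetry failed the null model test". The SAP describes variance components as the default against which compound symmetry was compared, so it is read here as independent errors.

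The only diagnostic reported is "Distribution of residuals was checked and met model assumptions for independence and normality", without a result. The SAP adds "Full code is available in Appendix A"; that appendix is not in the text available for this review.

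Protocol section 12.0 plans a mixed linear model with participant as the repeated factor and names no covariance structure. Section 5.0 states that "each participant will serve as his/her own control". The hypothesis in section 2.2 is that acceptance of the flavor improves over 12 weeks. The Post-Pre change in liking at 0%, the unsweetened drink, bears on it most directly.

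**The concern.** The design is paired, yet the liking model as described gives the pairing no role. The reason given is that a test of one common correlation was not significant. With so few participants such a test often misses real dependence, and it is not aimed at the two patterns that matter most for a pre/post contrast:

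- **Participant-by-Concentration:** a participant has a lasting liking for a given sweetness. The plan looks at six levels "so that we can observe if a shift in ideal level of sweetness occurs after consuming the unsweetened waters", so an individual ideal is at least contemplated.
- **Participant-by-Time:** a participant's ratings move together between sessions. Protocol section 7.0 warns that "hunger makes energy containing foods more palatable, skewing sensory ratings", and provides a snack to limit this.

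Compound symmetry contains neither pattern, so JAR shares the weakness. The first pattern makes the model's standard error too large, and a real gain at 0% could be missed. The second makes it too small for the overall Time effect, and chance could pass for change. A check on the distribution of residuals tests neither.

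**Working it through.** **Inputs.** Six concentrations and two times come from the SAP. The values n = 13 and n = 16 come from the glucose calculation in protocol section 12.0. The documents give no SD, effect size or sample size for the ratings, so there is no figure of the plan's own to reproduce. Assumed: residual SD 30, a 25-point gain, one rating per cell, two-sided 5%. Write P, PC, S and E for the participant, participant-by-Concentration, participant-by-Time (session) and residual SDs.

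**1. What the null-model test can show.** For balanced data the REML likelihood ratio is 12(n−1)·ln MST − (n−1)·ln MSP − 11(n−1)·ln MSW, compared with 3.841. MSP, MSW and MST are the between-participant, within-participant and pooled mean squares. At n = 13 the test is non-significant when MSP/MSW = F lies between 0.387 and 2.122.

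- Estimated common correlation (F−1)/(F+11): −0.613/11.387 = −0.054 to 1.122/13.122 = 0.085.
- Ratio of pre/post standard errors, compound symmetry over variance components, √(12/(F+11)): 1.027 to 0.956.

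So the switch between the two structures, taken alone, changes the standard error by +2.7% to −4.4%. But a true common correlation of 0.10 is missed in 46% of simulated trials at n = 13, and in 37% at n = 16.

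**2. Model standard error against true standard error.**

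- Post-Pre at one concentration: true variance 2(S²+E²)/n; variance components uses 2(P²+PC²+S²+E²)/n.
- Overall Time: true variance 2(S²+E²/6)/n; variance components uses 2(P²+PC²+S²+E²)/(6n).
- Compound symmetry replaces the bracketed total by E² + (10/11)PC² + (6/11)S².

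With the numbers put in (P = 0, E = 30):

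- At 0%, PC = 15: √(1125/900) = 1.118; compound symmetry √(1104.5/900) = 1.108.
- At 0%, PC = 30: √(1800/900) = 1.414; compound symmetry √(1718.2/900) = 1.382.
- Time, S = 10, PC = 0: √((1000/6)/(100+150)) = 0.816; compound symmetry √((954.5/6)/250) = 0.798.
- Time, S = 10, PC = 30: √((1900/6)/250) = 1.125, now too large.

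For Time, the errors under variance components cancel when P² + PC² = 5S². At S = 10 and P = 0 that is PC = √500 = 22.4.

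**3. Power and type I error.** Simulation of 20,000 trials per case at n = 13, P = 0, kept only where the null-model test was non-significant, as the SAP reports for liking. VC is variance components; CS is compound symmetry.

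| Case | VC | CS | Paired |
|---|---|---|---|
| Power at 0%, PC 15 | 46–47% | 47% | 49% |
| Power at 0%, PC 20 | 41% | 41% | 49% |
| Power at 0%, PC 30 | 26% | 27% | 49% |
| Type I at 0%, PC 30 | 0.6% | 0.7% | 5% |
| Type I Time, S 10, PC 0 | 11% | 11% | 5% |
| Type I Time, S 10, PC 15 | 8% | 8% | 5% |
| Type I Time, S 10, PC 30 | 3% | 3% | 5% |

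The test is non-significant in 92%, 89% and 79% of trials at PC 15, 20 and 30 (S = 0). At n = 16 and PC 30, power is about 33% (VC) against 59% (paired). For JAR, with compound symmetry in all trials, power at 0% is 28% against 50% at PC 30, and type I error for Time is 11.6% at S = 10 with PC = 0.

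**4. If ratings are independent.** The noncentrality is 25/√(2·900/13) = 25/11.77 = 2.12. Power is 56% on 12 × 12 = 144 degrees of freedom (VC) and 50% on 12 (paired). VC is then correct and the paired test costs about 6 points.

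**The case against.** The other side has real substance.

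- **The code is unseen.** Appendix A may already fit a participant effect. That stands, and is why the point concerns the model as described. A random intercept alone, however, behaves like compound symmetry and would not supply the missing terms.
- **The documents do not establish either pattern.** The hunger remark concerns foods containing energy, so its effect would depend on sugar level. It is not clearly a shift of all ratings, and it need not apply to the 0% drink. The ideal sweetness level is named because it may move, not because it is stable. The protocol also controls the test through warm-up tastings, counterbalanced order, rinsing, breaks and, for remote sessions, an instruction not to be hungry. All of this stands.
- **The large power loss is a special case.** It needs a participant-by-Concentration SD equal to the residual SD and little general participant effect. Adding a participant SD of 10 or 20 to that case cuts the chance of the reported test result from 79% to 48% or 8%. At SD 15 the loss is small.
- **One rating per cell may be wrong.** Protocol section 3.2.a includes replicates of the unsweetened and fully sweetened drinks. It is unclear whether the first tastings were rated, and the doubt falls on 0%.
- **Concentration-by-Time is not inflated.** A session shift common to all concentrations cancels from that term. With session SD 10, type I error under variance components was 3.3%.

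A reader might infer that the liking results are wrong, or that dropping compound symmetry made them falsely significant. The documents support neither: the switch alone moves the standard error by a few percent, and the direction of any error depends on unreported variances. Nor does the SAP depart from protocol section 12.0, which fixes no covariance structure.

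**Conclusion.** The point holds in a limited form. A non-significant test of one common correlation, in a sample of the size the protocol suggests, does not show that an adolescent's liking ratings are independent. Neither rating model, as described, allows participant-specific responses to Concentration or Time. The pre/post standard errors for liking and JAR are therefore not shown to be reliable; they are not shown to be wrong.

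The possible effect runs from none to material. The loss at 0% is 2 to 3 points of power in one assumed case and 23 points in another. The overall Time test can be anti-conservative (about 11%) or conservative (about 3%). Every SD, the 25-point gain, the sensory sample size and the single rating per cell are assumptions. This is a minor point on a secondary outcome. The paired t-tests for glycemia do not use these models.

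**What to change.** 1. Check the code in Appendix A. If a participant effect is already fitted, correct the SAP text to say so.
2. Unless the terms below are already there, keep participant in both models by design and not by the outcome of the null-model test. Re-run with participant, participant-by-Concentration and participant-by-Time random effects and Kenward-Roger degrees of freedom. Drop an interaction component estimated at zero, and report that.
3. Add a participant-level paired Post-Pre comparison of liking at 0% as a supporting analysis, and state how any replicate ratings are handled.
4. State the number of participants with sensory data, and show the present variance-components and compound-symmetry results beside the new ones.

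The cost is SAP wording and a re-run on existing data. Some intervals may widen. Components may be estimated at zero: participant-by-Time was zero in about 54% of simulated runs without a session effect, and the Time test was then slightly conservative (3.3% to 3.7%). The paired test loses power if ratings are independent (50% against 56%), which is why it is supporting only. The random-effects model itself lost almost nothing in that case (about 56%). That check used truncated ANOVA estimates with Satterthwaite degrees of freedom as a stand-in for the Kenward-Roger fit.
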